3.5 Informed Consent

Written informed consent will be obtained from patients prior to any research-related procedures. Full disclosure of the nature and potential risks of participating in the trial is to be made.

3.6 Randomization Method

Women will be randomized to either an inpatient or outpatient cervical ripening procedure using a computer generated randomization scheme through REDCap.

3.7 Investigational Drugs

Cervidil has FDA approval for hospital cervical ripening.

3.7.1 Investigational New Drug Application/Exemption

3.7.1.a

This protocol may need an Investigational New Drug Application (IND) as Cervidil has approval for inpatient use, and this study will evaluate the use of Cervidil in both inpatient and outpatient settings.

3.7.1.b

The risks to the participant is minimal, as the product is lawfully marketed as a prescription drug product, and this study does not utilize a route of administration or dosage level different than the current approved use of the product.

3.7.1.c

Even though published research indicates minimal risk for outpatient use, because outpatient use is not an indication listed on the package insert an IND will be obtained.

3.7.2 Drug Administration

Participant will come to labor and delivery prior to her induction. Cervidil 10mg timed release insert will be placed in the posterior vaginal fornix. The Cervidil will remain in place until the participant returns to continue the induction procedure (12 hours maximum.)

3.7.3 Concomitant Medications

- 1. Excluded medications include other uterotonics (example: oxytocin) while Cervidil remains in place.
- 2. Known hypersensitivity to prostaglandins.

3.7.4 Drug Compliance

- 1. Participants will call Labor & Delivery if the insert does not stay in place prior to returning to L&D.
- 2. Upon admission to Labor and Delivery for induction, the RN will check for and remove the Cervidil and will notify study staff if any problems were noted with participant compliance.
- 3. Patient will call L&D immediately for any other study related concerns.

3.7.5 Drug Accountability

Drug accountability, including inventory, will be recorded using a drug accountability log.

4 – STUDY PROCEDURES

4.1 Screening for Eligibility and Recruitment

All women scheduling an induction with cervical ripening are potentially eligible for the study. Inclusion/exclusion criteria will be reviewed with the patient's chart.

The following methods of recruitment may be used:

- Participants will be referred to study personnel personally or by the offices of their Obstetric providers.
- Participants will be screened for eligibility by one of the investigators by review of submitted study participation form/prenatal record and electronic medical records.
- Study recruitment materials such as brochures and fliers may be used throughout the studies. As they are developed, these will be submitted to the IRB for approval.

If a patient appears to meet the criteria for the trial, she will be told about the study and asked for written informed consent to participate in the trial. Consent may be obtained any time after her induction is scheduled.

4.2 Study Procedures

Eligible and consenting patients will be randomized by a certified research staff member using an internet based randomization system maintained by the Women and Newborn Research department. The patient will be assigned to either the inpatient or outpatient cervical ripening group. Patients will be consented and randomized at the time the patient is being scheduled for their induction. If for any reason a research staff member is unavailable to consent the patient at the time the induction is being scheduled, a time will be set for the Cervidil placement as well as a time for the induction and consent/randomization will be scheduled prior to Cervidil placement. If they are randomized to the "inpatient group" then the following induction appointment will be cancelled.

When the participant comes in for their scheduled induction, eligibility criteria will be verified again.

4.2.1 For participants randomized to the Outpatient cervical ripening arm:

- The patient will be an outpatient in L&D ("place in observation" status in iCentra) and placed on the fetal monitor. The clinician or hospitalist will perform an ultrasound for assessment of amniotic fluid volume by deepest vertical pocket (DVP) and review the fetal heart tracing. If the fetal heart rate is reactive (Category I) and the DVP is > 2cm the procedure may proceed once ordered by the attending obstetric provider or OB hospitalist.
- 2) Nursing or research staff member completes the outpatient cervical ripening case report form (CRF).
- 3) The cervix is examined and Bishop score is documented: Requirements of exam to do cervical ripening
 - a. Cervix is dilated less than 3cm
 - b. Presenting part is vertex
 - c. The provider places the Cervidil into the posterior vaginal fornix with the string at the introitus.

- d. The provider is available for immediate phone consultation by the patient or nursing staff and is readily available to L&D.
- 4) The patient is watched with continuous fetal monitoring for 2 hours.
- 5) The patient is discharged to home if all of the following are present:
 - a. Category 1 tracing X2 hours.
 - b. No vaginal bleeding
 - c. Normal maternal vital signs.
 - d. Intact BOW
 - e. Less than 1 contraction every 10 minutes at the time of discharge.
- 6) The patient remains for further evaluation if any of the following are noted. (If the patient must remain for any of these reasons, she will need an evaluation by her attending MD or the Hospitalist prior to discharge.):
 - a. Category 2 or 3 tracing
 - b. Vaginal bleeding (beyond spotting from placement of Cervidil insert)
 - c. Any abnormal maternal vital signs (as defined in Intermountain Healthcare Standard Practice Guidelines)
 - d. ROM
 - e. More than 1 contraction every 10 minutes is noted in the last 30 minutes of monitoring.
 - f. If the insert is inadvertently dispelled from the vagina, a new insert should be placed within 15 minutes and the participant may still be discharged if she meets criteria. (The vaginal insert releases prostaglandin at a rate of 0.3 mg/hr so replacing the insert within 15 minutes will not change the overall effect of the medication)
- 7) Patient will remove the insert and return to the hospital:
 - a. For spontaneous rupture of membranes
 - b. For vaginal bleeding
 - c. Consistent contractions closer than every 10 minutes
 - d. Severe pain
 - e. Decreased fetal movement
 - f. Temperature over 100.5 degrees F.
- 8) When admitted to L&D for induction as outpatient in a bed:
 - a. Admission history and physical is done by labor nurse
 - b. Cervidil is removed and Bishop score is documented.
 - c. Results of exam are given to the attending provider.
 - d. If appropriate, Pitocin induction of labor is started per Intermountain Healthcare Standard Practice Guidelines.
- 9) Cervidil placement should not exceed 12 hours.
 - a. Management of induction per Intermountain Healthcare Standard Practice Guidelines continued at the discretion of the admitting provider.
 - b.

4.2.2 For participants randomized to the inpatient cervical ripening arm:

The patient is scheduled in L&D for:

1) Admission as "outpatient in a bed" in iCentra for hospital placement of Cervidil.

- a. The patient's priority is based on the maternal and fetal condition compared to other scheduled inductions.
- 2) Induction of labor.

Preadmission:

The patient will have education and consent to the procedure prior to admission.

- The patient will be admitted to L&D ("outpatient in a bed" status in iCentra) and placed on the fetal monitor. The clinician or hospitalist will perform an ultrasound for assessment of amniotic fluid volume by deepest vertical pocket (DVP) and review the fetal heart tracing. If the fetal heart rate is reactive (Category I) and the DVP is > 2cm the procedure may proceed once ordered by the attending obstetric provider or OB hospitalist.
- 2) Nursing or research staff member completes the outpatient cervical ripening CRF.
- 3) If the fetal heart rate is reactive (Cat I) and the DVP is >2cm the procedure may proceed once ordered by attending obstetric provider or OB Hospitalist.
- 4) The cervix is examined: Requirements of exam to do cervical ripening
 - a. Cervix is dilated less than 3cm
 - b. Presenting part is vertex
 - c. The provider places the Cervidil into the posterior vaginal fornix with the string at the introitus.
 - d. The provider is available for immediate phone consultation by the patient or nursing staff and is readily available to L&D.
- 5) The patient is watched with continuous fetal monitoring for 2 hours.
- 6) The patient remains hospitalized
 - a. If the insert is inadvertently dispelled from the vagina, a new insert should be placed within 15 minutes and the participant may still be discharged if she meets criteria.
 (The vaginal insert releases prostaglandin at a rate of 0.3 mg/hr so replacing the insert within 15 minutes will not change the overall effect of the medication)
- 7) The Cervidil may be removed and induction of labor per Intermountain Healthcare Standard Practice Guidelines may be started per discretion of the admitting provider for any of the following:
 - a. For spontaneous rupture of membranes
 - b. For vaginal bleeding
 - c. Consistent contractions closer than every 10 minutes
 - d. Severe pain
 - e. Decreased fetal movement
 - f. Temperature over 100.5 degrees F.
 - g. Document dat/time of Cervidil removal
 - h. Document Bishop score
- 8) Cervidil placement should not exceed 12 hours.
 - a. Management of induction per Intermountain Healthcare Standard Practice Guidelines continued at the discretion of the admitting provider.

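### Section 4.2.2 step 6a allows an inpatient-arm woman to be discharged during ripening, although its parent step keeps her in hospital

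*Combined protocol and SAP*

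**What the plan says.** All references are to the combined protocol and SAP. Section 3.6 has women "randomized to either an inpatient or outpatient cervical ripening procedure", so the place of ripening is the assigned treatment.

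For the outpatient arm, section 4.2.1 sets out a full route home:

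- Step 5 opens with "The patient is discharged to home if all of the following are present" and lists five conditions.
- Step 6 lists reasons to keep her for further evaluation. Its item f says that if the insert comes out, "a new insert should be placed within 15 minutes and the participant may still be discharged if she meets criteria".
- Step 7 opens with "Patient will remove the insert and return to the hospital" and lists the triggers.

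For the inpatient arm, section 4.2.2 schedules admission "in iCentra for hospital placement of Cervidil", followed by induction. After placement and two hours of monitoring, step 6 states "The patient remains hospitalized". Its single sub-item, 6a, covers an expelled insert and again says "the participant may still be discharged if she meets criteria".

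**The concern.** Step 6 and step 6a tell bedside staff different things about the same woman at the same moment. The parent line keeps her in hospital; the sub-item permits her to leave on criteria that her arm's procedures never state.

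Three things are at stake:

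- **Treatment separation.** A woman sent home under 6a would receive the other arm's treatment while apparently following her own arm's procedure. The primary outcomes in section 4.4.1 are time from admission to complete dilation and hospital cost, and both depend on where ripening takes place.
- **Deviation status.** Section 4.3.1 requires deviations to be recorded and evaluated for IRB reporting. Step 6 makes the discharge a breach and step 6a allows it, so a monitor could not classify the event from the protocol.
- **Off-label use.** Section 3.7.1.c notes that outpatient use is not on the package insert and that an IND will be obtained for this reason. The inpatient procedures should not authorise outpatient use by accident.

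**Working it through.** The point is textual. It depends on no significance level, power, effect size or standard deviation, and the plan gives no figure to reproduce. The check compares the two arms' procedures.

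| Element | Outpatient, 4.2.1 | Inpatient, 4.2.2 |
|---|---|---|
| Instruction after two hours of monitoring | Discharge home if step 5 is met | Stay in hospital (step 6) |
| Criteria for discharge during ripening | Five (5a to 5e), plus the reasons to stay in step 6 | None |
| Expelled-insert sentence with discharge clause | Step 6f | Step 6a, same wording |
| Instructions to remove the insert and return | Step 7 | None; step 7 leaves removal to the admitting provider |

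1. **Is the wording the same?** Yes. Steps 6f and 6a match, including the bracketed note on the 0.3 mg/hr release rate. The clause occurs twice in the current text, once where it belongs and once where it does not.

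2. **Does the clause have anything to refer to in 4.2.2?** No. That section gives no criteria for discharge during ripening. To act on 6a, staff would have to borrow them from 4.2.1.

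3. **Could it mean ordinary discharge after delivery?** No. The sentence concerns replacing an insert within 15 minutes, while ripening is in progress.

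4. **Is there other evidence of copying?** Yes. Step 2 of 4.2.2 has staff complete the outpatient ripening form. That the clause was carried over is an inference, but the matching text and the absent criteria support it strongly.

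5. **Is an inpatient route home set out elsewhere?** No. Where consent is deferred, section 4.2 says that for a woman assigned to the inpatient group "then the following induction appointment will be cancelled". This fits an arm in which nobody goes home and comes back.

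6. **How large could the effect be?** The documents give no rate of expulsion or of discharge after replacement, so the expected number of cases cannot be calculated. Section 2.2 plans 100 women in the inpatient arm, so each case is 1/100 = 1 percentage point of that arm.

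7. **Could a case be found afterwards?** Yes. Section 6.3 lists the time the woman went home and the time of readmission among the data elements.

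**The case against.** The strongest reply is that this is an editorial slip that would mislead nobody. The arm's intent is clear. Step 6 is an unqualified directive, whereas 6a is only a conditional permission; since 4.2.2 supplies no criteria, the clause may have nothing to operate on. Section 1.3 mentions a manual of operations with more detailed procedures, and section 8.1 provides for staff training, so bedside staff may never act on 6a.

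The safety side can also be overstated. Section 3.7.4 tells participants to call Labor and Delivery if the insert does not stay in place or if they have other study concerns. Section 3.7.2 caps placement at 12 hours. Section 2.4.1 says participants will be trained to remove the insert. Section 3.4.1 requires them to live or stay less than 20 minutes away. The cancelled appointment is the separate later slot on the deferred-consent route only, and 4.2.2 still schedules the woman for induction.

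Most of this stands, and it limits the size of the problem. The general provisions narrow the gap in return instructions, although they do not reproduce the trigger list in 4.2.1 step 7. The cancelled appointment carries little weight as a harm. The manual is not among the documents, so what it says on this point is unknown.

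None of it removes the conflict. Clear intent makes the correction uncontroversial, but the operative text still contains a permission that the arm's design excludes. Being able to trace a case afterwards does not tell a nurse which line to follow.

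**Conclusion.** The concern holds: step 6a of section 4.2.2 is wrong as written. It permits discharge under a parent step that requires the woman to stay, on criteria that the section does not contain.

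The importance is low. A crossover needs an expelled insert, a replacement and a decision to discharge despite step 6, all in the same woman. The 1 percentage point per case rests on the 100 women per arm in section 2.2 and describes a hypothetical case; it does not estimate how many there will be. No figure for bias, dilution or power is claimed, and the design, analysis and sample size are unaffected. The correction is worth making because it protects the assigned contrast and settles how such a discharge is classified, at almost no cost.

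**What to change.** In section 4.2.2 step 6a, delete the 11 words that begin with the conjunction before "the participant may still be discharged if she meets criteria" and run to the end of that sentence. Keep the 15-minute replacement instruction and the note on release rate. Leave section 4.2.1 step 6f unchanged.

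Step 6a then says only that an expelled insert is replaced, under a step that keeps the woman in hospital. Any discharge home during ripening in this arm becomes a protocol deviation under section 4.3.2 without further interpretation.

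The cost is one deleted clause and the approval by the Principal Investigator and IRB that section 1.3 requires for any change. Sample size, data collection and timeline are not affected.

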4.3 Event Reporting

Adverse events, unanticipated problems and intercurrent illnesses will be documented in REDCap when reported by the participant or the RN caring for the patient during labor. Follow up by her physician will continue throughout the duration of her hospital stay. Serious Adverse Events (SAE's) will be reported to both the FDA and to Ferring's safety mailbox [contact] within 24 hrs. Non-serious adverse events will be reported to Ferring cumulatively on a quarterly basis.

4.3.1 Adverse Events/Unanticipated Problems

Adverse events will be reported by submitting a completed adverse events form to the Principal Investigator.

The Investigator is responsible for identifying adverse events that occur to each subject during their participation in the study. An adverse event or unanticipated problem can occur at any time during the conduct of the study. An adverse event can be identified by the Investigator or reported by the subject.

Protocol deviations/violations may occur throughout the study. These must be recorded and evaluated for IRB reporting.

Definitions

- Adverse Event: An adverse event is any undesirable experience associated with the use of a medical product in a patient.
- Serious Adverse Event: An adverse event is serious when it involves a death, is lifethreatening, initial or prolonged hospitalization, disability or permanent damage, congenital anomaly/birth defect, required intervention to prevent permanent impairment or damage, any other serious event that may jeopardize the patient and may require medical or surgical intervention/treatment to prevent other outcomes.
- Unanticipated Problem: unforeseen event in terms of nature, severity, or frequency, given the research procedures and the subject population being studied

Reporting Requirements

Events must be reported to the IRB or sponsoring agency, per policy. All events are reported in the Event Reporting Portal in the Intermountain Healthcare Women and Newborn Research Department.

Unanticipated Problems: Reporting is required if the following criteria are met.

- a) unexpected -considering the research procedures described in the protocol, investigator's brochures and informed consent documents, and in consideration of the characteristics of the study population;
- b) is related or possibly related to the subject's participation in the research; and

c) Suggests that the research places subjects or others at greater risk of harm than was previously known or recognized.

Unanticipated problems will be recorded in the Event Reporting Portal that will be evaluated by the principal investigator or designee. This will include a summary of the event, correction of the deviation/violation, and a corrective action plan. The PI/designee will indicate if it is reportable to the IRB, per current IRB policy.

4.3.2 **Protocol Deviations/Violations**

Protocol Deviation/Violation: Accidental or unintentional changes to, or non-compliance with, the IRB approved protocol without prior IRB review and approval that could affect the subject's rights, safety, welfare, and/or the integrity of the resultant data, regardless of whether there was actual harm.

All events are reported in the Event Reporting Portal in the Intermountain Healthcare Women and Newborn Research Department. The Protocol Deviation Form that will be evaluated by the principal investigator or designee. This will include a summary of the event, correction of the deviation/violation, and a corrective action plan. The PI/designee will indicate if it is reportable to the IRB.

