7.2 Data Safety Monitoring Committee

The Data Safety Monitoring Committee (DSMC) will be compromised of at least 3 members who are not affiliated with the trial to monitor the maternal and fetal outcomes in the study. The DSMC will evaluate study data from the first five participants, including any reported adverse events. Thereafter, they will meet on a quarterly basis throughout the remainder of the study enrollment period of the study.

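### The adverse-event definition is tied to the product both arms share, so harm from the outpatient setting and fetal or newborn harm are not expressly covered

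*Combined protocol and SAP*

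**What the plan says.** All references are to the combined protocol and SAP.

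- **Definition (4.3.1):** "An adverse event is any undesirable experience associated with the use of a medical product in a patient". There is no clause admitting events regardless of relationship, and no mention of care setting, study procedures, fetus or newborn.
- **Who is covered (4.3.1):** "The Investigator is responsible for identifying adverse events that occur to each subject during their participation in the study". Section 3.4.1 enrols pregnant women.
- **Serious events (4.3.1):** these are defined as adverse events that meet a further criterion. The criteria include death and "initial or prolonged hospitalization, disability or permanent damage, congenital anomaly/birth defect", and end with a catch-all about danger to the patient.
- **Reporting (4.3):** serious events go to the FDA and the manufacturer within 24 hours, and non-serious events go to the manufacturer quarterly. The same section says: "Adverse events, unanticipated problems and intercurrent illnesses will be documented in REDCap when reported by the participant or the RN caring for the patient".
- **What is randomised (3.6):** "Women will be randomized to either an inpatient or outpatient cervical ripening procedure". Section 3.7.1 adds that "this study will evaluate the use of Cervidil in both inpatient and outpatient settings", and that an IND will be obtained because the package insert does not list outpatient use.
- **DSMC (7.2):** it is set up "to monitor the maternal and fetal outcomes in the study", and its review of the first five participants includes reported adverse events.

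**The concern.** An adverse-event definition should reach the harms that the experimental condition could cause. Here the drug is common to both arms and the experimental condition is the period at home, yet the definition asks about association with the product. Late recognition of a problem, delayed return, or birth before arrival could be attributed to the setting rather than to the insert, and so fall outside the definition. It is also left open whether harm to the baby counts.

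What is at stake is the expedited safety stream. An event that is not an adverse event cannot become a serious adverse event under 4.3.1. It then need not appear in the 24-hour reports or among the adverse events put before the DSMC. If inclusion depends on how generously an investigator reads the wording, it may also differ between investigators and between the two hospitals named in 7.1.1.

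**Working it through.** No arithmetic applies; the check is a reading of the sections against each other.

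**Step 1: what differs between arms.** Sections 4.2.1 and 4.2.2 place the same insert in both arms, with two hours of continuous monitoring after placement. After that, women in one arm may go home and women in the other stay. The contrast is setting (3.6), and the setting is the reason given for the IND (3.7.1).

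**Step 2: what each channel asks for.**

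| Channel | Entry condition | Harm attributed to the setting | Fetal or newborn harm |
|---|---|---|---|
| Adverse event (4.3.1) | Association with a product, in a patient | Only if also seen as associated with the insert | Only if fetus or newborn is read as a patient |
| Serious event and 24-hour report (4.3, 4.3.1) | Must first be an adverse event | As above | Express only for birth defect; death is listed without saying whose |
| Unanticipated problem (4.3.1) | Unforeseen, given the research procedures and population | Recorded if unforeseen | Recorded if unforeseen |
| Intercurrent illness (4.3) | Reported by participant or nurse | Does not naturally describe delayed care | Not stated |
| Outcomes and data elements (4.4.2, 4.4.3, 6.3) | None | Delivery mode, time of and reason for readmission | Apgar, weight, cord pH if done; NICU admission as an outcome in 4.4.3 |
| DSMC (7.2) | Maternal and fetal outcomes, plus reported adverse events | Outcomes seen; adverse events only if they pass the first row | Same |

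**Step 3: does the unanticipated-problem route close the gap?** Its relationship criterion, "is related or possibly related to the subject's participation in the research; and", refers to the research rather than the product, which suits a setting trial. That criterion and its two companions govern when reporting is required; recording in the Event Reporting Portal does not depend on them. However, the definition itself requires the event to be unforeseen. Fetal distress is a listed product risk in 2.4.1, and bleeding, membrane rupture, fever and reduced fetal movement are listed reasons to return in 4.2.1. Such events can be classed as foreseen. The route helps but does not replace an all-cause definition.

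**Step 4: do the collected outcomes close it?** They record several results that matter without passing through the adverse-event definition. They are not expedited reports, though. The list in 6.3 has no item for fetal or neonatal death, place of birth or maternal complications. Reason for readmission records why a woman came back, not what harm followed.

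**Step 5: is there an all-cause safety table elsewhere?** None is described. Section 5.3 prespecifies no adverse-event comparison, and 7.2 does not ask for events by arm regardless of relationship.

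**The case against.** The strongest reply is that a sensible investigator would report most of these events anyway, and much of it stands.

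- *Associated with* is weaker than *caused by*. A woman at home normally still has the insert in place (3.7.2), so many events there could be called associated with it.
- The definition says *a patient*, not the enrolled woman. The birth-defect criterion can only concern the offspring, and death is not limited to the mother. A reader might infer that newborn harm is excluded outright; the text does not say so. It leaves the question open.
- A reader might infer that setting-related or newborn harm goes uncounted altogether. That is too strong. Unanticipated problems and intercurrent illnesses are recorded; Apgar, NICU admission and delivery mode are outcomes; reason for readmission is collected; and the DSMC's remit is wider than adverse events.
- A reader might infer that the safety comparison is pulled toward no difference. The documents do not support this. The planned comparisons of Apgar, NICU admission and delivery mode do not use the definition, and no comparison of adverse events by arm is prespecified.
- Sections 4.3 and 4.3.1 describe no separate step at which an investigator rules adverse events related or unrelated, so a systematic filter cannot be assumed.

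The reply does not show that the wording covers these harms. It shows that they would often be captured by interpretation or by another route. For 24-hour serious-event reports, where the adverse-event definition is the only entry, that is not enough.

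**Conclusion.** The point holds as a partial gap in adverse-event and expedited reporting. The definition is anchored to what the arms share and does not expressly reach the element that is randomised and outside the package insert, nor fetal or newborn harm other than birth defect. Such events may be left out of adverse-event records, 24-hour serious-event reports and the adverse events shown to the DSMC.

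No number can be put on it. The documents give no rate of setting-related harm, and even an assumed rate would show only how many such events might occur, not how many the definition would exclude. The conclusion rests on a literal reading of 4.3.1 and on at least some events being attributed to the setting alone. It does not imply bias in the planned outcome comparisons. It is a cheap improvement to a safety rule.

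**What to change.** 1. In 4.3.1, define an adverse event as any untoward medical occurrence in a randomised woman, her fetus or her newborn during study participation, whether or not considered related to the insert. The serious-event definition then inherits this scope.
2. On the adverse-event form, record relationship to the insert and relationship to the assigned setting as two separate fields.
3. Give the DSMC, and report at the end of the trial, all events by randomised arm regardless of relationship.
4. State when study participation ends for this purpose: 4.3 describes follow-up during the hospital stay, whereas 8.2 follows participants for three months after delivery. These should be reconciled.

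The cost is protocol wording and one extra form field. The downside is more recorded events, most of them obstetric and unrelated to either insert or setting. Treatment and outcome definitions are unchanged.
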